7.1.2. Main analytical approach

The following descriptive summaries will be provided for all the 3 cohorts:

- N (number of subjects in the population), n (number of subjects used for the analysis), arithmetic mean, 95% CI (90% CI for Cohort 3 only) for the arithmetic mean, SD, median, minimum, maximum for the untransformed data.
- Geometric mean, 95% CI (90% CI for Cohort 3 only) for the geometric mean, SD of log_e-transformed data and %CVb or %CVw for the untransformed data (except Tmax and T_{1/2}).

7.1.2.1. Intercurrent Events and handling of missing data

The intercurrent events mentioned in Section 1.1.2. along with the corresponding strategies will be considered during this analysis.

- For treatment discontinuation due to any reason:

Subjects' data available up to the withdrawal will be included in the descriptive PK summaries. If a subject withdraws consent during a period, the missing data post withdrawal will not be imputed.

The derived PK parameters for e.g., AUC, Cmax etc. of that partially completed period will be calculated, if data permits.
- For Subject use concomitant/prohibited medication:

The subject data post consumption of concomitant/prohibited medications (intercurrent event) will be analyzed as collected.

If multiple intercurrent events are observed, then the data will be handled using more than one strategy as described in Section 1.1.2 and interpretations of the results will be made accordingly.

Graphical presentations will be provided, if appropriate. All data will be listed. Details of the planned displays are provided in the Output Programming Specification (OPS) document. Data Displays will be based on GSK Data Standards and statistical principles.

7.2. Statistical analysis for comparison of food effect

7.2.1. Endpoints/Variables

To assess the food effect in Cohort 3 only, statistical analysis will be based on AUC(0-t), AUC (0- ∞) and Cmax.

7.2.2. Main analytical approach

Log_e-transformed data will be statistically analyzed using a mixed model with:

- fed or fasted status, period and their interaction term (if tested as significant) as fixed effects.
- subject as random effect
- Only data of subjects participating in Cohort 3 both periods will be included in this analysis, all other dose level data from Cohorts 1 and 2 will be excluded from this analysis.
- The Kenward and Roger method for approximating the denominator degrees of freedom and correcting for bias in the estimated variance-covariance of the fixed effects will be used.
- An unstructured type of the covariance matrices R (accounting for the within subject variability) and G (accounting for the between subject variability) will be used.
- Distributional assumptions underlying the model used for analysis will be examined by obtaining a normal probability plot of the residuals and a plot of the residuals versus the fitted values (i.e., checking the normality assumption and constant variance assumption of the model respectively) to gain confidence that the model assumptions are reasonable.
- If there are any departures from the distributional assumptions, alternative transformations, such as data squared or square root of data, will be explored.
- Non-parametric analyses will be conducted if the normality assumption does not hold for any of the alternative transformations.
- If this model fails to converge, alternative covariance structures may be considered in the following order (1) Compound Symmetry (CS) and (2) Variance Components (VC).

Model Results:

- The estimated mean differences and 90% CIs of (fed – fasted) will be presented based on the log_e-transformed data.

- The estimated geometric mean ratios and 90% CI of (fed: fasted) after back-transformation will also be presented.

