6.3. Measures to Minimize Bias: Randomization and Blinding

6.3.1. Randomization

On Day 1, participants will be assigned a unique number (randomization number) in ascending numerical order. The randomization number encodes the participant's assignment to either GSK3494245 or placebo, according to the randomization schedule generated prior to the study by the Statistics Department at GSK, using validated internal software.

All participants will be randomized using the Clinical Unit's internal procedure. Details of their randomisation procedure are described in the SRM and study communications plan.

Study treatment will be dispensed at the study visits summarized in SoA. Each participant will be dispensed blinded study treatment, labelled with his unique randomization number, throughout the study. Returned study treatment should not be re-dispensed to the participants.

In the SAD part (Cohorts 1, 2 and 3a) participants will be randomized in a 3:1 ratio to either GSK3494245 or placebo per period. In the MAD part (Cohorts 4-8) participants will be randomised to receive repeat doses of either GSK3494245 or placebo in a 3:1 ratio. In Cohort 3 (SAD part), all participants will receive GSK3494245 as well as placebo. They will be randomized to one of the 4 sequences with up to 4 participants per sequence (see [Table 7](#)) in a 1:1:1:1 ratio.

Table 7 Cohort 3

Sequence	Period 1	Period 2	Period 3	Period 4
1	DL X Fasted	P Fed	DL X Fed	P Fasted
2	DL X Fed	DL X Fasted	P Fasted	P Fed
3	P Fasted	DL X Fed	P Fed	DL X Fasted
4	P Fed	P Fasted	DL X Fasted	DL X Fed

Once a randomization number has been assigned to a participant, it cannot be reassigned to any other participant.

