	
 apparent terminal phase half-life ($t_{1/2}$) 
from MAD:
 
 Day 1 AUC(0-t), AUC(0-∞), AUC(0-tau), C_{max}, T_{max}, $t_{1/2}$, trough concentration (C_{tau}). 
Trough concentration (C_{tau}) samples collected on the specified days may be used to assess attainment of steady state.
 
To estimate the extent of accumulation after repeat dosing, the observed accumulation ratio for AUC (($RAUC_{(0-tau)}$)), C_{max} (RC_{max}) and C_{tau} (RC_{tau}) may be determined. To estimate time-invariance after repeat dosing, the ratio of AUC(0-tau) on Day 7 to AUC(0-∞) on Day 1 may be obtained. Time-invariance ratio calculation for TID regimen, if conducted, as AUC(0-tau) on Day 6 evening dose to AUC(0-∞) on Day 1
 
Statistical analyses of the pharmacokinetic parameter data will be the responsibility of Biostatistics, GlaxoSmithKline. No formal hypotheses will be tested. Pharmacokinetic data will be presented in graphical and/or tabular form and will be summarized descriptively. Full details on the statistical aspects will be detailed in the Reporting and Analysis Plan (RAP).
 
A population PK approach may be used if data permit. In this case the analysis may be reported separately from the clinical study report.
 
Estimand
 
Intercurrent events, the estimand strategy to handle these events and the changes to the respective analysis to implement the strategies will be highlighted in the RAP.
 
Food Effect (SAD part)
 
The effect of food on the pharmacokinetics of GSK3494245 will be examined. AUC(0-t), AUC(0-∞) and C_{max} of GSK3494245 will be analyzed after a \log_e-transformation of the data. An analysis of variance model will be fitted along with 90% confidence intervals using a mixed effects model, with fed/fasted condition as a fixed effect and participant as a random effect. Point estimates and corresponding 90% confidence intervals will be constructed for the comparisons of interest of GSK3494245 fed – GSK3494245 fasted, using the residual variance. These will then be back-transformed to provide point estimates and corresponding 90% confidence intervals for the geometric mean ratios fed: fasted.

Endpoint	Statistical Analysis Methods

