	
In the event the DEC decide there is a need to address any concerns from a safety or PK point of view, the 4th dose level (DL4) may be repeated at the start of Cohort 2. Thereby allowing up to 7 dose levels to be studied, in this scenario. In addition, the DEC may decide, based on emergent safety and PK data to include an additional cohort of up to 8 participants following the same design as Cohorts 1 and 2.
 
Food Effect:
 
Cohort 3 will consist of up to 16 healthy participants and will comprise of a 4-way crossover in which participants will receive GSK3494245 and placebo in both fasted and fed conditions. The selected dose level (DLX) to investigate the effect of food on the safety, tolerability, and PK of a single dose of GSK3494245 will be one already evaluated from a previous intervention period.
 
Cohort 3a will comprise of 4 intervention periods, investigating 4 dosing regimens under fed conditions. Participants will receive three doses of GSK3494245 and a randomised placebo dose, administered in the fed state.
 
Washout: At least 48 hrs. or 5-half-lives (whichever is longer) will be given between each dose for an individual participant.
 
Note: Participants will be admitted to the unit the day before dosing (Day -1) and will remain in the unit overnight until Day 4 of intervention.
 
MAD:
 
The MAD part will be a twice-daily (BID) or three-times daily (TID) 7-day repeat dose design in up to 5 cohorts (Cohorts 4, 5, 6, 7 and 8), each including 8 participants. Dependent on whether a food effect is observed in the SAD phase, the MAD part may also include drug administration after either fed or fasted conditions. Up to a maximum of 5 dose levels will be studied in the MAD part. CCI
 
Note: Participants will be admitted to the unit the day before dosing (Day -1) and will remain in the unit overnight until Day 8.

Dosing	
Dose Escalation (SAD):
 
 For Cohorts 1 and 2, each participant will receive a maximum of 3 ascending oral doses of GSK3494245 and 1 placebo dose under fasted conditions (4 regimens) in a crossover manner.

Overview of Study Design and Key Features	

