8. SAMPLE SIZE DETERMINATION

The planned sample size is up to 80 participants for this study (8 participants each for Cohorts 1, 2 and 3a up to 16 participants for Cohort 3) and up to 40 participants for the MAD part (8 participants into each of Cohorts 4-8). Additional participants may be recruited as replacements for withdrawn participants. Cohort 1, 2 and 3a are split by a 2:6 ratio of placebo participants to active participants per period. For Cohort 3 regimens are split by a 1:1:1:1 ratio.

For Cohorts 1, 2, 3a, and 4-8 assuming a between-participant CV (CV_b) of 30% for clearance, it is estimated that, with 6 participants per dose, the 95% CI around the mean of the clearance for a dose would lie within 36% of the point estimate.

Sample size in Cohort 3 was calculated based on the precision estimate for fed versus fasted status. The objective of Cohort 3 (SAD part) is to determine if food effects the PK of GSK3494245 and to inform the dosing regimen for the MAD part. A precision estimate was therefore used to determine the sample size, based on assumed within subject coefficient of variation (CV_w) for AUC of 20% and C_{max} of 30% respectively. A maximum of 16 participants will be recruited with the aim of getting evaluable data from 12 participants. If the estimates for the CV_w decrease following review of the data from Cohorts 1 and 2, then fewer participants may be recruited, with the aim of obtaining as few as 10 evaluable participants. The number of planned evaluable participants will not be less than 10, nor will the number of recruited participants be greater than 14.

Assuming a point estimate for fed versus fasted status of 1 (i.e., no food effect), under the variability assumptions described above, and a sample of 12 evaluable participants, the precision estimates and 90% CI for AUC and C_{max} are:

Parameter	CV _w	Sample size	Precision estimate	90% CI
AUC	20%	12	16%	(0.84, 1.19)
C _{max}	30%	12	24%	(0.76, 1.32)

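### The food-by-period interaction pre-test in SAP 7.2.2 is fully aliased with sequence in Cohort 3, and the stated food-effect precision matches a model without the SAP's period term (minor)

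*SAP*

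**What the plan says.** SAP 7.2.2 analyses log-transformed AUC(0-t), AUC(0-∞) and Cmax from Cohort 3 in a mixed model with "fed or fasted status, period and their interaction term (if tested as significant) as fixed effects" and subject as a random effect. There is no sequence term, no significance level for the pre-test, and no statement of how period is coded. It specifies "The Kenward and Roger method for approximating the denominator degrees of freedom" and restricts the data as follows: "Only data of subjects participating in Cohort 3 both periods will be included in this analysis". SAP 1.2 nevertheless describes four periods: "Cohort 3 will consist of up to 16 healthy participants and will comprise of a 4-way crossover".

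Protocol 6.3.1 says of Cohort 3 participants: "They will be randomized to one of the 4 sequences with up to 4 participants per sequence". Table 7 then sets out the four sequences, each with two active and two placebo periods.

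The protocol's own food-effect model (9.5.2) has neither period nor interaction. It is a mixed model "with fed/fasted condition as a fixed effect and participant as a random effect".

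SAP 8 and protocol 9.2 give precision for "a sample of 12 evaluable participants, the precision estimates and 90% CI for AUC and" Cmax as 16% and 24%, from assumed within-subject CVs "for AUC of 20% and C_{max} of 30% respectively". Neither document states the degrees of freedom used.

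**The concern.** Only the active records enter the fed-versus-fasted comparison, so each participant contributes two observations, both determined by his sequence. A food-by-period interaction needs fed and fasted results in the same period that can be compared free of group differences. Table 7 does not provide this, because within any period the fed and fasted active results come from different sequences. The plan would let the data choose the model through a test whose result has no clear meaning, separately for three endpoints, in an estimation-only analysis.

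The second issue is consistency. The SAP adds a period term that the protocol model lacks but carries over the same precision figures. If those figures belong to the model without period, they are slightly optimistic for the model the SAP will fit.

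**Working it through.** **Inputs.** Active periods from protocol Table 7; within-subject CVs of 20% (AUC) and 30% (Cmax) and evaluable n of 12, or as few as 10, from SAP 8; two-sided 90% confidence from SAP 7.2.2. The between-participant CV of 30% used below is the value SAP 8 states for clearance.

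**1. Active records by sequence**

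| Sequence | Fasted active | Fed active | Fed minus fasted estimates |
|---|---|---|---|
| 1 | P1 | P3 | F + (P3 − P1) |
| 2 | P2 | P1 | F + (P1 − P2) |
| 3 | P4 | P2 | F + (P2 − P4) |
| 4 | P3 | P4 | F + (P4 − P3) |

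Here F is the food effect on the log scale. The eight food-by-period cells each occur once, in one sequence.

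**2. Aliasing.** Ranks of the design matrix at three participants per sequence (24 active records):

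| Terms | Rank |
|---|---|
| food + period | 5 |
| food + period + interaction | 8 |
| food + period + sequence | 8 |
| food + period + interaction + sequence | 8 |
| participant + food + period | 16 |
| participant + food + period + interaction | 16 |

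Once food and period are fitted, the interaction and sequence span the same 3-df space. With participant effects in the model the interaction adds nothing, so all its information is between participants. If period instead means a two-level order term, the within-participant rank is 14 with or without the interaction, so the same conclusion holds.

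**3. Power of the test.** As an illustration, take a food ratio of 1.5 in periods 1-2 and 1.0 in periods 3-4, n=12, between-participant CV 30% and within-participant CV 20%. Power is about 13% at the 5% level and 23% at the 10% level.

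**4. Effect on the food estimate.** The four sequence contrasts in step 1 sum to 4F, because the period terms cancel. Food plus three period differences therefore use up all four contrasts, and the within-participant food estimate is their unweighted mean. With 3 per sequence its standard error (CV 20%) is 0.0809 with or without the interaction. With a 3,3,2,2 split it is 0.0904 with the interaction and 0.0901 without.

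**5. Degrees of freedom.** Within participants at n=12, food alone leaves 24 − 13 = 11 (n-1). Food plus four-level period leaves 24 − 16 = 8 (n-4). With participant random, a Satterthwaite calculation without the interaction gives 8.04 to 8.11 at a between-participant CV of 30%. A two-level order term leaves 24 − 14 = 10 (n-2).

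**6. Reproducing the stated precision.** With SDw = √ln(1+CVw²), i.e. 0.198 and 0.294, precision = exp(t × SDw × √(2/n)) − 1. For n=12 and t(0.95, 11) = 1.796 this gives 15.6% and 24.0%, the plan's 16% and 24%. With n-1 df it matches all 18 distinct values in the sensitivity table; with n-2 it matches 10, and with n-4 it matches 5.

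**7. Restated with n-4 df.** From step 4, √(2/n) becomes √(2 × Σ(1/n_s)/16), where n_s is the number in each sequence. The t quantiles are 1.860 at n=12 and 1.943 at n=10.

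| n (split) | n-1 df, AUC / Cmax | n-4 df, AUC / Cmax |
|---|---|---|
| 10 (3,3,2,2) | 17.6% / 27.2% | 19.2% / 29.7% |
| 12 (3,3,3,3) | 15.6% / 24.0% | 16.2% / 25.0% |
| 14 (4,4,3,3) | 14.2% / 21.7% | 14.7% / 22.5% |
| 16 (4,4,4,4) | 13.1% / 20.0% | 13.3% / 20.3% |

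**The case against.** The best defence is that little depends on this. SAP 7.2.2 lists as results only the overall fed-minus-fasted difference and the fed:fasted ratio, and step 4 shows that these hardly depend on whether the interaction is kept. The food effect is a secondary, estimation-only analysis, and the current protocol already sets fed dosing for the MAD part. All of that stands, and it keeps the point minor.

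Three stronger readings are tempting, and the documents do not support them:

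- *The interaction test is pure noise.* Participant is random and sequences are randomised, so the test does use between-participant information and has some power (step 3). The fault is confounding and weakness. A significant result could be chance, carry-over or a real interaction.
- *The trial will report a food effect that changes over time.* Nothing in the SAP's list of model results says so.
- *The printed 90% intervals are too narrow.* They are wider than n-4 df gives. At n=12, n-4 gives (0.86, 1.16) for AUC and (0.80, 1.25) for Cmax, against printed (0.84, 1.19) and (0.76, 1.32). The printed limits equal 1−p and 1/(1−p), where p is the precision figure; that is a separate matter. Only the precision column is optimistic.

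The n=10 comparison also needs its condition. Ten evaluable participants are planned only if the within-subject CVs prove lower than assumed. With n-4 df and a 3,3,2,2 split, CVs of about 16.5% and 24.6% would restore 15.6% and 24.0%. Dropout from up to 16 recruits could also leave 12 participants unequally split.

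**Conclusion.** The concern holds as a minor one. The interaction step in SAP 7.2.2 cannot be interpreted under Table 7 and should not decide the model. That conclusion does not depend on whether period is coded with four levels or two.

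The degrees-of-freedom point is conditional and small. It assumes period is a four-level factor, a single within-participant variance, and the stated CVs. SAP 7.2.2 names an unstructured covariance first, which was not modelled here. That the plan used n-1 is inferred from the agreement of all 18 figures and from protocol 9.5.2; it is not written. At n=12 the AUC figure still rounds to 16% and Cmax moves from 24% to 25%. At n=10 split 3,3,2,2, Cmax moves from 27% to about 30% if the CV stays at 30%.

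**What to change.** - In SAP 7.2.2, delete the interaction and its significance test. Prespecify food status and period (four-level factor) as fixed effects, with participant as a random effect.
- Replace the reference to both periods with both active (fed and fasted) periods.
- Align protocol 9.5.2 with this model, so that the two documents agree and the precision figures have one source.
- Restate the Cohort 3 precision column in SAP 8 and 8.1 and in protocol 9.2 and 9.3 with n-4 df, stating the sequence split assumed. Ten and 14 cannot be divided equally over four sequences.

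The cost is text edits and one recomputed column, with slightly less favourable stated precision. Recruitment, randomisation and conduct do not change.

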4.1.3. Initiation of Food Effect (SAD part, Cohort 3)

Cohort 3 will consist of up to 16 healthy participants. The selected dose level (DLX) to investigate the effect of food on the safety, tolerability and PK of a single dose of GSK3494245 will be one already evaluated from a previous intervention period. The maximum exposure following fed administration should not exceed the highest safe exposure explored in fasted conditions. The decision on the dose level of GSK3494245 to be administered will be made by the dose escalation committee (DEC). In this Cohort, participants will also receive two doses of placebo, in the fed and fasted states

respectively, in order to gain more information of background changes in safety parameters.

Table 1 Study Duration of Cohorts 1-3, 3a

Screening	All screening assessments to be completed within 28 days prior to first dose.
Intervention Period	
Cohorts 1 and 2 will comprise of 4 intervention periods, investigating 4 dosing regimens under fasted conditions. Participants will receive three doses of GSK3494245 and a randomised placebo dose, administered in the fasted state.
 
Cohort 3 will comprise of 4 intervention periods, investigating a single dose of GSK3494245 in both fasted and fed conditions and also two doses of placebo also given under fasted and fed conditions.
 
Cohort 3a will comprise of 4 intervention periods, investigating 4 dosing regimens under fed conditions. Participants will receive three doses of GSK3494245 and a randomised placebo dose, administered in the fed state.
 
Each regimen will consist of a single dose given on Day 1, with participants in-house for 4 nights and 5 days. Participants will be admitted to the unit the day before dosing (Day -1) and will remain in the unit overnight until Day 4, when they will be discharged after completion of all assessments.

Washout Period	At least 48 hrs or 5-half-lives (whichever is longer) between each dose for an individual participant.
Follow-up	At least 7 days and no greater than 14 days after last study drug administration. If warranted, additional follow-up visits may be scheduled.
Total duration	Cohorts 1, 2, 3 and 3a will be approximately 15-16 weeks each.

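### SAP 7.2.2 pairs a random subject effect with unstructured R and G, which two active-drug records per participant cannot identify; the effect on the food-effect CI depends on how R is indexed, which the SAP does not say

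*SAP*

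**What the plan says.** SAP 7.2.2 models loge AUC(0-t), AUC(0-∞) and Cmax with fed/fasted status and period as fixed effects, adding their interaction if significant. It then lists:

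- "subject as random effect";
- "An unstructured type of the covariance matrices R (accounting for the within subject variability) and G" (the between-subject matrix), both in the one model;
- Kenward-Roger degrees of freedom;
- a fallback if the model does not converge: "alternative covariance structures may be considered in the following order (1) Compound Symmetry (CS) and (2) Variance Components (VC").

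On the data used it says: "Only data of subjects participating in Cohort 3 both periods will be included in this analysis". Cohort 3 has four periods, but Protocol 4.1.3 (Table 1) describes them as "investigating a single dose of GSK3494245 in both fasted and fed conditions and also two doses of placebo". Placebo periods yield no drug AUC or Cmax, so each participant supplies two values per parameter.

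Protocol 9.5.2 gives a simpler model, "with fed/fasted condition as a fixed effect and participant as a random effect", and bases the 90% CI on the residual variance. The SAP does not say whether R is indexed by condition or by period, whether the fallback applies to R, G or both, or whether the random subject term is removed under the unstructured (UN) or CS options.

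**The concern.** A random subject intercept adds the same amount to every variance and covariance within a participant. An unstructured R, or a CS R, already contains a term that does this. Fitting both gives a likelihood with a flat direction. The only safeguard is non-convergence, yet an optimiser can stop normally on a flat surface, so the move to a simpler structure may never be triggered.

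The cohort's product is a fed:fasted ratio with a 90% CI. The planned precision rests on a single within-participant variance. If the structure fitted depends on how a programmer indexes R, or on how the software handles a redundant parameter, the analysis is not fully pre-specified.

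**Working it through.** **1. The plan's own figure.** Inputs from SAP section 8: CVw 20% (AUC) and 30% (Cmax), 12 evaluable, 90% two-sided. SDw = √ln(1 + CVw²); half-width h = t(0.95, n−1) × SDw × √(2/n); precision = exp(h) − 1.

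- AUC: SDw = 0.198; h = 1.796 × 0.198 × 0.408 = 0.145; precision 15.6% (stated 16%).
- Cmax: SDw = 0.294; h = 1.796 × 0.294 × 0.408 = 0.215; precision 24.0% (stated 24%).

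The precision figures in the sensitivity table reproduce too. The formula has one within-participant variance, which is the VC structure.

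**2. R by fed/fasted condition.** The data inform only the 2×2 marginal covariance V. With random-intercept variance g:

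- UN R: V11 = g + r11, V22 = g + r22, V12 = g + r12. Adding c to g and subtracting c from each r leaves V unchanged.
- CS R: diagonal = g + c + σ², off-diagonal = g + c. Only g + c is determined.
- VC: diagonal = g + σ², off-diagonal = g. Both are determined.

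| Structure | Parameters | Identified |
|---|---|---|
| UN R + random subject | 4 | 3 |
| CS R + random subject | 3 | 2 |
| VC (random subject + residual) | 2 | 2 |
| UN R, no random subject | 3 | 3 |
| CS R, no random subject | 2 | 2 |

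**3. Does it move the result with R by condition?** In one simulated data set (12 participants, 2 records each), −2 REML was −23.9795 for g = 0, 0.02, 0.04 and 0.06 with R shifted to compensate. The estimate stayed at 0.0189 and its SE at 0.0405. Under CS plus random subject the value was −21.5131 however the covariance was split, with the same estimate and SE 0.0400, as under VC. Across 200 data sets with period in the model, UN and VC estimates agreed to rounding error and the mean SE ratio was 1.014.

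A Kenward-Roger check on the Table 7 design (3 per sequence, period in the model, g at 0, 0.02, 0.05 and 0.08, two generalised inverses) left the adjusted SE at 0.08062 and the df at 8.043. CS with random subject gave 0.08062 and 8.042, identical to VC. In 300 simulations at CVw 20%, the mean 90% half-width was 15.6% (UN) against 15.5% (VC) at n = 12, and 18.6% against 18.3% at n = 10.

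**4. R by period.** Active periods by sequence, from Protocol Table 7: sequence 1 has periods 1 and 3; sequence 2 has 1 and 2; sequence 3 has 2 and 4; sequence 4 has 3 and 4. Pairs 1-4 and 2-3 never occur in one participant. Observable moments: 4 variances + 4 covariances = 8. Parameters: 10 in a 4×4 unstructured R + 1 for g = 11. Dropping the random subject leaves 10 against 8.

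At 12 evaluable (3 per sequence) each observed covariance rests on three participants; at 10 (3, 3, 2, 2) some rest on two. A small refit, 25 data sets per size, put correlations on the boundary in about a third of data sets at n = 12 and nearly all at n = 10, with a more variable estimate and unstable SEs. That is enough to show direction, not to give a size.

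**The case against.** The strongest reply is that the natural reading of R is by fed/fasted condition, and there nothing reported changes: V is identified, the ratio and CI are practically those of VC, and the fallback list ends at VC anyway. This stands for that reading, and three stronger inferences a reader might draw therefore fail.

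- *Only VC can be identified.* Not so. UN or CS for R by condition is identified once the random subject term is dropped, and CS applied to a 1×1 G is simply VC.
- *Kenward-Roger results are unreliable.* Not shown in general. The information matrix for the covariance parameters is singular, but with a generalised inverse the SE and df did not move. No software failure has been demonstrated.
- *The CI widens by a known amount if R is by period.* Giving each sequence its own variance of the fed-fasted difference would produce a figure, but that is not the SAP's model: it ignores that period variances are shared across sequences. No figure is offered here.

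The protocol also defers technical detail to the analysis plan, so a richer SAP model is not in itself a contradiction, and the SAP's period term is absent from the protocol model. There is no formal hypothesis or equivalence margin, and the protocol's MAD dosing is already fed, so no formal decision turns on the CI width. These points limit severity. They do not settle the indexing of R or remove the redundancy.

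**Conclusion.** Wrong as written, low severity. The primary covariance model is over-parameterised (3 of 4 identified with R by condition), as is the CS fallback if it applies to R and the random subject term stays (2 of 3). The convergence trigger need not detect either.

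With R by condition, the ratio and 90% CI are practically unaffected; what has no unique value is the split into within- and between-participant variance, which matters only if the %CVw summary in SAP 7.1.2 is taken from this model. With R by period, which the SAP leaves open, the fit is close to degenerate at 10 to 12 evaluable participants and the estimate and SE can differ materially from the single-variance model.

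This assumes that subject means a random intercept, that the two periods in SAP 7.2.2 are the two active ones, and that the simulated conditions resemble the study. The period-indexed result rests on a small run.

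**What to change.** In SAP 7.2.2, replace the R/G bullet and the fallback list with a random participant intercept and a single residual variance (VC) as the primary covariance structure. This agrees with the covariance structure in Protocol 9.5.2 and with the precision calculation; the SAP's fixed effects can stay.

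If the sponsor wants UN or CS for R as an alternative, for example to allow unequal fed and fasted variances, state that R is indexed by fed/fasted condition and that the random subject term is then dropped.

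The cost is a line or two of SAP text before database release, with no change to data, design or sample size.
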